8.2 PSA Response

PSA will be used as an indicator of response in all disease categories. Changes in PSA will be assessed utilizing the following guidelines:

Assessment of response requires two PSA values ≥ 4 weeks apart. PSA must be assessed >4 weeks after prostatic biopsy.

Complete response:

Normalization (< 4 ng/ml (non prostatectomy) < 0.2 ng/ml (prostatectomy) of PSA on three successive determinations.

Partial response:

$>50\%$ decrease in PSA, persistent for ≥ 4 weeks and without clinical or radiological evidence of disease progression during this time period.

Progression: Increase in PSA to $\geq 50\%$ above baseline, if maintained ≥ 4 weeks.

Relapse from response or progression:

>50% increase above the nadir at a minimum of 5 ng/mL (i.e. PSA must rise a minimum of 5 units).

If that criterion is reached patients will be declared to have PSA Progressive Disease (PD), **but:**

- a. If radiographs do not confirm PD
- b. PSA and symptoms are stable or improved from baseline
- c. Patient is in agreement

Investigator will have the discretion to continue investigational therapy until:

PSA achieves a level of >50% of baseline

or

Radiographic or symptomatic PD

or

Patient wish to discontinue

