11. Concomitant use of phenytoin, carbamazepine, barbiturates, rifampicin, phenobarbital, or St John's wort, alfentanil, alfuzosin, almotriptan, alprazolam, amiodarone, amitriptyline, amprenavir, aprepitant, aripiprazole, bepridil, bortezomib, bosentan, budesonide, buprenorphine, buspirone, carbamazepine, cilostazol, cisapride, cyclosporine, delaviridine, didanosine, digoxin, disopyramidedofetilide, donepezil, eletriptan, elperenone, fluticasone,

fosamprenavir, galantamine, systemic griseofulvins, indinavir, levobupivacaine, lopinavir, midazolam, mifepristone, modafinil, nateglinide, nefazadone, nelfinavir, oxcarbazepine, pimoziide, quetiapine, quinidine, repaglinide, rifabutin, rifampins, rifapentine, ritonavir, saquinavir, sildenafil, sirolimus, tacrolimus, tadalafil, tolterodine, theophyllines, tolterodine, trazolam, valdecoxib, vardenafil, ziprasidone, zanisamide, statins, with the exception of pravastatin (Pravachol) or other "statins" which are not metabolized by or induce CYP3A4, calcium channel blockers, and macrolides or other agents that will be significantly perturbed in a clinically important way by the P450 inhibitory properties of ketoconazole

12. Concomitant use of proton pump inhibitors or H2 blockers
13. Treatment with a non-approved or investigational drug or agent within 28 days before day 1 of trial treatment.
14. Any unresolved chronic toxicity greater than CTC Grade 2 from previous anticancer therapy.
15. Incomplete healing from previous oncologic treatments or other major surgery.
16. Inability to swallow oral capsules.
17. Patients on digoxin will be excluded from this study.

Products Dosage and Mode of Administration

- Ketoconazole, 200 mg tablets, 2 tablets orally TID
- Calcitriol (0.5 mcg caplets) given orally QD X3 consecutive days every week
- Hydrocortisone 20mg AM, 10mg PM orally starting in the evening before the first dose of Calcitriol.

Number of Patients and Duration of Treatment

Number of patients expected to be enrolled each month: 2-3 patients

Total number of patients expected to enroll: 15 patients

Treatment will continue as long as there is absence of prohibitive toxicities and lack of clinical or radiological progression.

Estimated Time to Complete Accrual: 1 year

Statistical Analysis:

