5.10 Criteria for Discontinuation

Patients may be discontinued from trial treatment and assessments at any time at the discretion of the investigator(s). Specific reasons for discontinuing a patient from this trial are the following:

- Disease progression
- Intercurrent illness that prevents further administration of treatment
- Unacceptable AE
- Patient develops kidney stones
- Patient decides to withdraw from the study
- General or specific changes in the patient's condition render the patient unacceptable for further treatment in the judgment of the investigator

PSA progression is an increase of 50% above the nadir at a minimum of 5 ng/mL. (i.e. PSA must rise a minimum of 5 units)

If that criterion is reached patients will be declared to have PSA Progressive Disease (PD), **but:**

- a. If radiographs do not confirm PD
- b. PSA and symptoms are stable or improved from baseline
- c. Patient is in agreement

Investigator will have the discretion to continue investigational therapy until:

PSA achieves a level of $> 50\%$ of baseline

or

Radiographic or symptomatic PD

or

Patient wish to discontinue

The two options for categorizing withdrawal are either progressive disease (PD) or an AE (>1AE may be documented as a reason for withdrawal). Only 1 event will be captured as the cause of death. Note that death is an outcome and not an AE.

All trial treatment-related toxicities and SAEs must be followed up until resolution.

All patients who have new or worsening CTC Grade 3 or 4 laboratory values at the time of withdrawal must have further tests performed, and the results must be recorded appropriately. Until the laboratory values have returned to CTC Grade 1 or 2, unless these values are not likely to improve because of the underlying disease. In these cases, the investigators must record their opinions in the patients' medical records. Laboratory abnormalities should **not** be reported as AEs unless any criterion for a SAE is fulfilled, the laboratory abnormality causes the patient to discontinue from the study, or the investigator insists the abnormality should be reported as an AE.

At withdrawal all ongoing study-related toxicities and SAEs must be followed until resolution, unless in the investigator's opinion, the condition is unlikely to resolve due to the patient's underlying disease.

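### A PSA stable at baseline already exceeds the limit on continuing treatment after PSA progression, and nothing says which of two PSA-progression definitions applies to which patient

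*Combined protocol and SAP*

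**What the plan says.** Three places carry the same continuation rule: section 5.10 (Criteria for Discontinuation), section 8.2 (PSA Response) and Appendix B 2.2.6 (Tumor markers). Once PSA progression is declared, the investigator may keep the patient on therapy if radiographs do not confirm progression, "PSA and symptoms are stable or improved from baseline", and the patient agrees. Continuation ends when "PSA achieves a level of >50% of baseline", on radiographic or symptomatic progression, or at the patient's wish.

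PSA progression itself is defined as follows:

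- **Sections 8.2 and Appendix B 2.2.6, under Progression:** a rise of at least 50% "above baseline, if maintained ≥ 4 weeks".
- **Section 8.2, under the heading "Relapse from response or progression":** ">50% increase above the nadir at a minimum of 5 ng/mL (i.e. PSA must rise a minimum of 5 units", with no hold. Appendix B 2.2.6 has an equivalent rule under the same heading.
- **Section 5.10:** only "PSA progression is an increase of 50% above the nadir at a minimum of 5 ng/mL".

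Two other places bear on when treatment stops. Section 4.2 (Duration of Experimental Therapy) lists disease progression and points to section 6.3 for it, but 6.3 is Hydrocortisone. The synopsis (Number of Patients and Duration of Treatment) continues treatment given "lack of clinical or radiological progression" and does not mention PSA.

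**The concern.** The continuation rule admits a patient on one condition and stops him on another that he may already meet. Two investigators applying it to the same PSA series could reasonably reach opposite decisions: one because the patient qualifies to continue, the other because the limit is already exceeded.

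The two progression definitions add a second source of disagreement. They use different reference values, only one has a minimum absolute rise, and only one needs confirmation. Progression ends treatment under 4.2 and 5.10, so time on treatment, the recorded reason for withdrawal and any report of PSA progression depend on which text is followed. The cross-reference in 4.2 and the synopsis do not resolve it.

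**Working it through.** No stated figure in the plan belongs to this point, so the check puts the rules on a common scale. Let B be baseline PSA and N the nadir, in ng/mL. The values of B and N below are illustrative assumptions.

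**Inputs**

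| Rule | Source | Expression |
|---|---|---|
| Entry to continuation | 5.10, 8.2, App. B 2.2.6 | PSA stable at or improved from B |
| End of continuation | same three | PSA > 0.5 × B |
| Nadir rule | same three | trigger T = max(1.5 × N, N + 5), no hold |
| Baseline rule | 8.2, App. B 2.2.6 | PSA ≥ 1.5 × B, held at least 4 weeks |

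**Step 1. PSA stable at baseline.** PSA ≈ B, which is 100% of baseline and twice the 50% limit. The stop condition is met at entry.

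**Step 2. PSA improved from baseline.** There is room to continue only if the nadir rule fires below the limit, T < 0.5 × B. Both parts of T must satisfy this:

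- 1.5 × N < 0.5 × B gives N < B/3.
- N + 5 < 0.5 × B gives N < 0.5 × B − 5.

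The two bounds meet where B/3 = B/2 − 5, that is at B = 30. From 30 upward the one-third bound decides; below 30 the 5-unit minimum does.

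| Baseline B | Nadir must be below | As share of B |
|---|---|---|
| 100 | 33.3 | one third |
| 30 | 10 | one third |
| 20 | 0.5 × 20 − 5 = 5 | 25% |
| 10 | 0.5 × 10 − 5 = 0 | never |

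Examples:

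- B = 100, N = 45: T = max(67.5, 50) = 67.5, against a limit of 50. A PSA of 68 is progression, is improved from baseline, and is already past the limit.
- B = 100, N = 20: T = max(30, 25) = 30. Continuation is possible between 30 and 50.
- B = 10, N = 1: T = max(1.5, 6) = 6, against a limit of 5. No room.

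A PSA partial response needs a fall of more than 50%. A partial responder whose nadir lies between one third and one half of baseline (a fall of 50 to 67%) therefore has no room at any baseline.

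**Step 3. The two definitions of progression.** They can disagree in either direction.

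- B = 100, N = 60, PSA = 91: T = max(90, 65) = 90, so this is progression by nadir. By baseline it would need 150, held 4 weeks.
- B = 5, PSA never below baseline (N taken as 5): the baseline rule is met at 7.5 if held 4 weeks; the nadir rule needs max(7.5, 10) = 10.

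**Step 4. Design figures.** Section 12.0 states average probabilities of 10% (declared active) and 39% (early stop) at a 10% response rate, and 93% (declared active) at 40%. With stage-1 size n1 = 7 to 11, total n = 13 to 17 and the cut-offs r in the 12.0 table (2 for n = 13–14, 3 for n = 15–17):

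- P(early stop) = (1 − p)^n1.
- P(active) = sum over x ≥ 1 of Bin(x; n1, p) × P(Y > r − x), with Y ~ Bin(n − n1, p).

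Averaged over the 25 combinations, these give 9.7%, 39.2% and 93.5%, in agreement. They depend on response counts alone; no PSA-progression rule enters them.

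**The case against.** Several points can be made for the plan, and some stand.

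- **The rule is not empty.** After a deep fall it works as written (B = 100, N = 20). A reader might infer that most patients would already be past the limit. The documents give no distribution of nadirs, so no frequency can be claimed.
- **Two definitions need not conflict.** Baseline could serve patients whose PSA never falls and nadir those who relapse after a fall; with no fall, both start from 1.5 × B. The documents do not support that split: the nadir heading also covers progression, and 5.10 gives the nadir rule for everyone. What remains is unclear scope, not two rules that could never coexist.
- **The limit may have been meant as a rise above baseline.** That would put it at 1.5 × B, three times the written value. No passage says so, and the same wording appears in all three places.
- **Effect on the primary endpoint.** A reader might infer that the rules decide who is evaluable or who responds. The evaluability rule in 12.2 concerns objective tumor response, a secondary endpoint. PSA progression is not part of the PSA response definition in 8.2 or Appendix B. To lose a response this way, a patient must rise past the nadir trigger, be taken off, and be one who would later have fallen below half of baseline. No frequency is given for that path. The 23 to 143 days to a 50% PSA fall (mean 65) in section 2.3.1 come from calcitriol with dexamethasone, a different regimen, and do not describe responses after a rise.
- **The synopsis.** It does not say that clinical or radiological progression is the sole reason to stop, and a synopsis need not repeat 5.10. It is incomplete on PSA rather than contradictory.
- **Discretion is built in.** Section 5.10 lets the investigator discontinue a patient at any time, so some variation in off-treatment times is expected. That does not explain a limit incompatible with its own entry condition.

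**Conclusion.** The point holds as a drafting inconsistency in treatment rules. For a PSA stable at baseline, the continuation limit contradicts its entry condition outright. For an improved PSA, the rule works only below the nadir cut-offs in the working, which follow from the written thresholds including the 5 ng/mL minimum rise; how many patients get there is unknown.

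The scope of the two progression definitions is also unsettled, and they can classify the same patient differently. The consequence is inconsistent times off treatment and inconsistent reporting of PSA progression. It does not reach the error rates in 12.0, and an effect on the PSA response rate could arise only through time on treatment and is not shown.

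**What to change.** Reconcile 5.10, 8.2 and Appendix B 2.2.6 so that the continuation limit is compatible with its entry condition and is worded identically in all three. In the same places, state which progression definition applies to which patients, its reference value and minimum rise, and whether confirmation is required. Correct the reference to section 6.3 in 4.2 (Duration of Experimental Therapy), and align the synopsis sentence on treatment duration. The choice of clinical rule belongs to the sponsor.

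The cost is an amendment to wording in five places. Sample size, decision cut-offs and the assessment schedule need not change on account of this point.

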9.0 SAFETY EVALUATION

9.1 Adverse Events

9.1.1 Definitions

An adverse event or adverse experience (AE) is any untoward medical occurrence associated with the use of a drug in humans, whether or not considered drug related. Therefore, an AE can be ANY unfavorable and unintended sign (including an abnormal laboratory finding), symptom, or disease temporally associated with the use of a medicinal (investigational) product, whether or not considered related to the medicinal (investigational) product (attribution of ‘unrelated’, ‘unlikely’, ‘possible’, ‘probable’, or ‘definite’).

An AE is considered “unexpected” if it is not listed in the investigator brochure or is not listed at the specificity or severity that has been observed; or if an investigator brochure is not required or available, is not consistent with the risk information described in the general investigational plan in other study-related documents.

9.1.1.1 Diagnosis Versus Signs and Symptoms

If known, a diagnosis should be recorded on the CRF rather than individual signs and symptoms (e.g., record only liver failure or hepatitis rather than jaundice, asterixis, and elevated transaminases). However, if a constellation of signs and/or symptoms cannot be clinically characterized as a single diagnosis or syndrome at the time of reporting, each individual event should be recorded as an AE or SAE on the CRF. If a diagnosis is subsequently established, it should be reported as follow-up information.

9.1.1.2 Adverse Events Occurring Secondary to Other Events

In general, AEs occurring secondary to other events (e.g., cascade events or clinical sequelae) should be identified by their primary cause. For example, if severe diarrhea is known to have resulted in dehydration, it is sufficient to record only diarrhea as an AE or SAE on the CRF.

However, clinically significant AEs occurring secondary to an initiating event that are separated in time should be recorded as independent events on the CRF. For example, if a severe gastrointestinal hemorrhage leads to renal failure, both events should be recorded separately on the CRF.

11.1.1.3 Abnormal Normal Laboratory Values

Only clinically significant laboratory abnormalities that require active management will be recorded as AEs or SAEs on the CRF (e.g., abnormalities that require study drug dose modification, discontinuation of study treatment, more frequent follow-up assessments, further diagnostic investigation, etc.).

If the clinically significant laboratory abnormality is a sign of a disease or syndrome (e.g., alkaline phosphatase and bilirubin 5 x the upper limit of normal associated with cholecystitis), only the diagnosis (e.g., cholecystitis) needs to be recorded on the Adverse Event CRF.

If the clinically significant laboratory abnormality is not a sign of a disease or syndrome, the abnormality itself should be recorded as an AE or SAE on the CRF. If the laboratory abnormality can be characterized by a precise clinical term, the clinical term should be recorded as the AE or SAE. For example, an elevated serum potassium level of 7 mEq/L should be recorded as “hyperkalemia”

Observations of the same clinically significant laboratory abnormality from visit to visit should not be repeatedly recorded as AEs or SAEs on the CRF, unless their severity, seriousness, or etiology changes.

11.1.1.4 Preexisting Medical Conditions (Baseline Signs and Symptoms)

A preexisting medical condition should be recorded as an AE or SAE only if the frequency, severity, or character of the condition worsens during the study. When recording such events on an Adverse Event CRF, it is important to convey the concept that the preexisting condition has changed by including applicable descriptors (e.g., “more frequent headaches”).

9.1.2 Grading and Relationship to drug

The descriptions and grading scales found in the CTEP Version 4.3 of the NCI Common Terminology Criteria for Adverse Events (CTCAE) will be utilized for AE reporting. CTEP Version 3 of the CTCAE is identified and located at:
http://ctep.cancer.gov/protocolDevelopment/electronic_applications/ctc.htm.

AEs not covered by specific terminology listed should be reported with common medical terminology, and documented according to the grading scales provided in the CTCAE Version 3.

The relationship of event to study drug will be documented by the Investigator as follows:

- **Unrelated:** The event is clearly related to other factors such as the participant’s clinical state, other therapeutic interventions or concomitant drugs administered to the participant.
- **Unlikely:** The event is doubtfully related to investigational agent(s). The event was most likely related to other factors such as the participant’s clinical state, other therapeutic interventions, or concomitant drugs.
- **Possible:** The event follows a reasonable temporal sequence from the time of drug administration, but could have been produced by other factors such as the participant’s clinical state, other therapeutic interventions or concomitant drugs.
- **Probable:** The event follows a reasonable temporal sequence from the time of drug administration, and follows a known response pattern to the study drug. The event cannot be reasonably explained by other factors such as the participant’s clinical state, therapeutic interventions or concomitant drugs.
- **Definite:** The event follows a reasonable temporal sequence from the time of drug administration, follows a known response pattern to the study drug, cannot be reasonably explained by other factors such as the participant’s condition, therapeutic interventions or concomitant drugs; AND occurs immediately following study drug administration, improves upon stopping the drug, or reappears on re-exposure.

9.1.3 Reporting Adverse Events

Table 1 Guidelines for Routine Adverse Event Reporting for Phase 1 Studies (Regardless of Expectedness)

Attribution	Grade 1	Grade 2	Grade 3	Grade 4
Unrelated	X	X	X	X
Unlikely	X	X	X	X
Possible	X	X	X	X
Probable	X	X	X	X
Definite	X	X	X	X

Table 2 Guidelines for Routine Adverse Event Reporting for Pilot, Phase 2, and Phase 3 Studies (Regardless of Expectedness)

Attribution	Grade 1	Grade 2	Grade 3	Grade 4
Unrelated			X	X
Unlikely			X	X
Possible	X	X	X	X
Probable	X	X	X	X
Definite	X	X	X	X

Routine AEs occurring between the start date of intervention until 30 days after the last intervention or until the event has resolved, the study participant is lost to follow-up, the start of a new treatment, or until the study investigator assesses the event(s) as stable or irreversible, will be reported. New information will be reported after it is received.

9.2 Serious Adverse Events

11.2.1 Definition

A serious adverse event (SAE) is any adverse event (experience) that in the opinion of either the investigator or sponsor results in **ANY** of the following:

- Death.
- A life-threatening adverse event (experience). Any AE that places a participant or participant, in the view of the Investigator or sponsor, at immediate risk of death from the reaction as it occurred. It does **NOT** include an AE that, had it occurred in a more severe form, might have caused death.
- Inpatient hospitalization or prolongation of existing hospitalization (for > 24 hours).
- A persistent or significant incapacity or substantial disruption of the ability to conduct normal life functions.
- A congenital anomaly or birth defect.
- Important Medical Event (IME) that, based upon medical judgment, may jeopardize the participant and may require medical or surgical intervention to prevent one of the outcomes listed above.

9.1.4 Reporting Serious Adverse Events

All new SAEs occurring from the date the participant signs the study consent until 30 days after the last intervention or a new treatment is started, whichever comes first, will be reported. During the screening period, only SAEs related to study procedures need to be reported. The SAE Source Form is to be completed with all available information, including a brief narrative describing the SAE and any other relevant information.

SAEs occurring after the 30 day follow-up period that the investigator determines to be possibly, probably or definitely related to the study intervention should be reported.

SAEs identified as an Unanticipated Problem by the Investigator must be reported. Please refer to Section 10.0 for details on reporting Unanticipated Problems

9.1.5 Follow-Up for Serious Adverse Events

All related SAEs should be followed to their resolution, until the study participant is lost to follow-up, the start of a new treatment, or until the study investigator assesses the event(s) as stable or irreversible. New information will be reported when it is received.

10.0 Unanticipated Problems

10.1.1 Definition

An Unanticipated Problem (UP) is any incident, experience, or outcome that meets all of the following criteria:

- Unexpected (in terms of nature, severity, or frequency) given:
 - a) The research procedures that are described in the study-related documents, including study deviations, as well as issues related to compromise of participant privacy or confidentiality of data.
 - b) The characteristics of the participant population being studied.
- Related or possibly related to participation in the research (possibly related means there is a reasonable possibility that the incident, experience, or outcome may have been caused by the procedures involved in the research).
- Suggests that the research places participants or others at a greater risk of harm (including physical, psychological, economic, or social harm) than was previously known or recognized and if in relation to an AE is also deemed serious

